2.5 Randomization and Blinding

This is an open-label study and does not involve randomization or blinding.

3 General Statistical Consideration

Categorical data will be summarized with counts and percentages. Percentages will be calculated based on the number of non-missing values and will be reported to one decimal place.

Continuous data will be summarized with descriptive statistics including the number of non-missing values, mean, standard deviation, standard error, median, minimum, and maximum. Minimum and maximum will be reported to the same precision as the raw values, mean and median will be reported to one additional decimal place, and standard deviation and standard error will be reported to two additional decimal places.

Non-flare-up based summaries will be performed based on visits in Table 1 and Table 2 in the protocol.

Flare-up based summaries will be performed based on flare-ups at flare-up visits: Flare-up Day 1, Flare-up Week 4 (28 days), Flare-up Week 12 (Day 84) etc.

To distinguish flare-up based analysis from subject based analysis, m will be used for number of flare-ups and n will be used for number of subjects.

In summary of change from baseline analysis for Enrolled Population, baseline from non-flare-up based treatment will be used for subjects in group PVO 20/10 mg only.

3.1 Definition of Baseline

Unless otherwise stated, baseline will be defined as Section 3.1.1 to 3.1.3.

3.1.1 Baseline for Non-Flare-up Based Treatment

- For subjects from Part B continuing non-flare-up based treatment into Part C (i.e., subjects who ever received at least one dose of non-flare-up based treatment in both Part B and Part C), baseline

will be based on assessment prior to first non-flare-up treatment in Part B. For subjects who continued from Part B into Part C a Part C baseline is defined as the first assessment in Part C.

- For subjects who did not receive any non-flare-up based treatment in Part B but start non-flare-up based treatment during Part C, baseline will be based on assessment prior to first non-flare-up treatment in Part C.

3.1.2 Baseline for Flare-up Based Treatment

For subject receiving flare-up based treatment in Part C, baseline values will be the last available value prior to or on the date of first dose of flare-up treatment with the cycle.

3.1.3 Baseline for Subjects Never Receive PVO Treatment in Part C

For subjects who never received any PVO Treatment in Part C, baseline is defined as the most recent non-missing measurement on Part C Study Day 1.

If baseline is missing in Part C, then baseline will be based on assessment prior to first non-flare-up treatment in Part B.

3.1.4 Baseline for Subjects who Restarted Palovarotene After Dosing interruption in Part C

For subjects who paused dosing either because of the partial clinical hold for subjects <14 years on December 4, 2019 or because of interruption after Study PVO-1A-301 crossed futility on January 24th 2020 and subsequently re-started palovarotene their re-start baseline is defined as the first assessments after re-start.

3.2 Part C Study Day, Flare-up Cycle Days and Non-Flare-up Days

3.2.1 Part C Study Day 1

For all subjects, Part C Study Day 1 is defined as the date of informed consent in Part C. Part C Study Day -1 will be the day immediately prior to Part C Study Day 1.

3.2.2 Flare-up Cycle and Flare-Up Cycle Day 1

- A Flare-up Cycle will include the first flare-up and any subsequent intercurrent flare-ups during the same dosing period.
- Flare-Up Cycle Day 1 is defined as the first day that study drug is administered for the first flare-up during that cycle.

3.2.3 Duration of Flare-up Treatment

For subjects receiving flare-up treatment, duration of flare-up treatment (days) is defined as total flare-up cycle dosing periods (days) across all flare-up cycles.

For a flare-up cycle, the flare-up cycle dosing period (days) is defined as days that subjects received flare-up based treatment and is calculated as (last dose date of the flare-up cycle – first date of the flare-up cycle – days where flare-up meds were not taken/interrupted during the flare-up cycle + 1).

3.2.4 Duration of Non-Flare-up Treatment

Based on study design, subjects are assumed to be on non-flare-up based treatment from the date they received first non-flare-up treatment unless they receive flare-up based treatment. Thus, duration of non-flare-up treatment (days) will be calculated as (last non-flare-up treatment date - first non-flare-up treatment

date – duration of flare-up treatment (days) - days where non-flare-up meds were not taken/interrupted + 1). Duration of flare-up treatment (days) is defined in 3.2.3.

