5.10 Compliance

Compliance is defined as (duration of treatment/expected duration of treatment). Calculation of duration of treatment is described in Section 3.2.3 and 3.2.4.

The expected duration of treatment is calculated as following:

- For non-flare-up treatment, expected duration of treatment is calculated as (last non-flare-up dose date – first non-flare-up dose date) – (sum of (all Flare-up cycle dosing periods)) + 1.
- For flare-up treatment, expected duration of treatment is calculated as total of expected flare-up cycle dosing periods across all flare-up cycles. Each expected flare-up cycle dosing period is defined as (last flare-up cycle dose date – first flare-up cycle dose date + 1).

Compliance will be summarized for the Treated Population with descriptive statistics. Compliance in category (<80%, ≥80%) will also be summarized for counts and percentages of subjects.

6 Efficacy Data

Unless otherwise stated, efficacy data will be summarized using Enrolled Population presented by groups: PVO 20/10 mg Only, PVO 5 mg, PVO Total and Never Received PVO Treatment. The PVO 20/10 mg Only group only includes subjects who did not take PVO 5 mg.

Imaging Reads

Imaging data includes results from low-dose WBCT scans (excluding head) and radiographs.

WBCT HO status and total HO volume or new HO volume will be summarized by visit. Those analysis will be included in the interim CSR. All other analysis will be presented in the final CSR.

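### Part C non-flare-up duration subtracts every flare-up cycle, even those outside the 5 mg dosing interval, so exposure is understated and can turn negative for subjects with such a cycle

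*SAP*

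**What the plan says.** All references are to the Part C SAP unless stated; 5 mg means the non-flare-up regimen, including weight-adjusted equivalents.

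- **3.2.4** rests on the premise that "subjects are assumed to be on non-flare-up based treatment from the date they received first non-flare-up treatment unless they receive flare-up based treatment". It takes the span from first to last 5 mg dose: "duration of non-flare-up treatment (days) will be calculated as (last non-flare-up treatment date - first non-flare-up treatment" date. From this it subtracts "duration of flare-up treatment (days) - days where non-flare-up meds were not taken/interrupted + 1". It refers to 3.2.3 for the meaning of flare-up duration.
- **3.2.3** says that "duration of flare-up treatment (days) is defined as total flare-up cycle dosing periods (days) across all flare-up cycles". Each cycle's dosing period is its last date minus its first date, less "days where flare-up meds were not taken/interrupted during the flare-up cycle + 1". It therefore counts dosed days only.
- **5.10** sets compliance as duration over expected duration. "For non-flare-up treatment, expected duration of treatment is calculated as" the first-to-last 5 mg span less the "sum of (all Flare-up cycle dosing periods)) + 1". The same section defines a separate expected cycle period in calendar days, but uses it only for flare-up compliance.
- **5.9.2, 5.9.3 and 5.10** all use these durations, for 5 mg exposure categories, total exposure and compliance split at 80%.

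**The concern.** The premise of 3.2.4 concerns time after the first 5 mg dose, yet the quantity subtracted covers every flare-up cycle. A cycle that lies wholly before the first or after the last 5 mg dose takes no days out of the interval, so subtracting it removes days on which 5 mg was scheduled.

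The plan foresees such cycles. Section 2.2 describes subjects who start 5 mg during Part C. Section 2.4 groups flare-up cycles whether or not 5 mg came first. Section 7.1 allows the first Part C dose to be flare-up drug. The dosing halts described in 1.2 and 2.3 could also leave a cycle as a subject's last treatment.

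There is a second, smaller gap. Because 3.2.3 counts dosed days only, undosed days inside a cycle stay in the 5 mg interval. Section 7.1, by contrast, removes whole flare-up cycles from the non-flare-up adverse event period. Section 5.7 plans to tabulate cycle interruptions of at least 14 days, so these days are expected.

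At stake are the descriptive exposure and compliance results for the affected subjects.

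**Working it through.** **Inputs.** The 84-day cycle is the plan's nominal length (2.3). All other day counts are illustrative assumptions, apart from the Part B example.

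**Notation.** N = last minus first 5 mg date + 1. S = dosed flare-up days over all cycles (3.2.3). I = missed 5 mg days.

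- Plan duration (3.2.4) = N - S - I
- Plan expected duration (5.10) = N - S
- Plan compliance = (N - S - I)/(N - S) = 1 - I/(N - S)
- Overlap-based versions replace S by G, the calendar days of cycles falling within the 5 mg interval, and count in I only missed 5 mg days outside those cycles.

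**Check against the plan's own figure.** Part C gives no worked example. The Part B SAP (5.9) has 174 days with one fully dosed 84-day cycle starting on Day 11. The formula gives 174 - 84 = 90 days, which matches the 90 days stated there. It is therefore correct for a fully dosed cycle inside the interval.

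**Cycle outside the interval (S = 84, G = 0)**

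| N | I | Plan duration | Overlap-based duration | Plan compliance | Overlap-based compliance |
|---|---|---|---|---|---|
| 365 | 0 | 365 - 84 = 281 | 365 | 281/281 = 100% | 100% |
| 365 | 10 | 271 | 355 | 271/281 = 96.4% | 355/365 = 97.3% |
| 60 | 0 | 60 - 84 = -24 | 60 | -24/-24 = 100% | 100% |
| 60 | 6 | -30 | 54 | -30/-24 = 125.0% | 54/60 = 90.0% |
| 90 | 10 | -4 | 80 | -4/6 = -66.7% | 80/90 = 88.9% |

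In the first row the shortfall is 84/365 = 23%. Total exposure (5.9.3) is 281 + 84 = 365 days instead of 365 + 84 = 449, so the outside cycle disappears from the total. The last row would put a subject at 88.9% into the below-80% category.

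The compliance formula gives three regimes:

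- I = 0: compliance is 100%, which is correct, unless N = S, where it is undefined.
- I > 0 and N > S: compliance is too low, because the denominator is too small. It is negative once I exceeds N - S.
- I > 0 and N < S: numerator and denominator are both negative, and compliance exceeds 100%.

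**Undosed days inside a cycle (N = 365, 84-day cycle inside, 20 days undosed, so S = 64 and G = 84)**

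- Undosed cycle days not entered as missed 5 mg days: 365 - 64 = 301 days instead of 365 - 84 = 281. Total exposure is 301 + 64 = 365 instead of 281 + 64 = 345. Compliance is 301/301 = 100%, which is correct.
- Undosed cycle days also entered as missed 5 mg days: 365 - 64 - 20 = 281 days, which is correct. Compliance is then 281/301 = 93.4% instead of 281/281 = 100%.

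Under either reading, one of the two results is wrong.

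**The case against.** The formula suits the course the design intends: 5 mg, then a cycle, then 5 mg again. For subjects continuing from Part B, 2.2 places Non-flare-up Day 1 in Part B, so if that date is used no Part C cycle can precede it. This stands. It narrows the problem to subjects who start 5 mg in Part C after a treated flare-up and those who never resume 5 mg after a cycle. It does not remove the problem, since the plan provides for the first group.

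A reader might infer that compliance is wrong for everyone with an outside or interrupted cycle, or that it commonly exceeds 100%. The documents do not support that. Section 5.10 subtracts the same dosed-day sum in numerator and denominator, so compliance stays at 100% when no 5 mg dose is missed (unless expected duration is zero), and with a long interval it moves little (96.4% against 97.3%). An interrupted inside cycle would push it above 100% only if the denominator were read in calendar days. Section 5.10 uses the term that 3.2.3 defines in dosed days and reserves calendar days for a separately named quantity.

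A reader might also take it as settled that undosed cycle days count as 5 mg exposure. Section 3.2.4 also subtracts days on which 5 mg was not taken, and no 5 mg is taken on those days either. The premise of 3.2.4 favours not entering them there but does not decide it, so this part is an ambiguity with a wrong result either way.

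Finally, the consequences are limited. No efficacy estimate uses these durations. The Flare-up Per Protocol Population uses flare-up compliance and has no formal analyses planned (4.4). Adverse event periods (7.1) and cumulative dose in mg (5.9.3) are defined separately. Negative durations would be visible in programming, but figures such as 281 instead of 365 would not.

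**Conclusion.** The point holds in limited form. Applied literally, 3.2.4 understates non-flare-up duration and total exposure for any subject with a flare-up cycle outside the first-to-last 5 mg interval. The shortfall equals that cycle's dosed days, 84 for one full nominal cycle, and the duration goes negative when those days exceed the interval. Compliance is distorted only when such a subject also misses 5 mg doses. It is then usually too low, negative when expected duration is small, and above 100% only when flare-up days exceed the whole 5 mg span.

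The treatment of undosed days inside a cycle is unsettled. Either exposure is overstated by those days or 5 mg compliance is understated.

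The sizes rest on the plan's 84-day cycle and on assumed interval lengths and missed days. The effect is confined to descriptive exposure and compliance tables, and the number of subjects affected cannot be known from the document.

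**What to change.** - In 3.2.4 and in the non-flare-up denominator of 5.10, subtract only the calendar days of flare-up cycles (last minus first cycle dose + 1, interruptions included) that overlap the interval from first to last 5 mg dose.
- Then, in 3.2.4 only, subtract missed 5 mg days that fall outside those cycles.
- Leave 3.2.3 as it is for flare-up exposure, where dosed days are the intended quantity.

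The cost is a few lines of SAP wording and a small change to one derivation. No new data are needed, since the formulas already use the dates and missed-dose days required.

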3.3 Definition of New-Onset Potentially Clinically Significant (PCS) Value

New-onset potentially clinically significant (PCS) values are defined as values that were not PCS at baseline and were PCS at post-baseline.

3.4 Adjustments for Covariates

As requested by US FDA during review of the US NDA, Ipsen is conducting multiple analyses comparing annualized new HO between Study 202 Part C and NHS, including

- GEE for new HO from all scans in Study 202 Part C, such that baseline is more than 30 days after the end of the previous flare-up, versus NHS. (Subjects without 2 WBCTs in Study 202 Part C where the first is at least 30 days after the end of the previous flare-up are not included.)
- GEE for new HO from all scans post-restart in Study 202 Part C, such that baseline is more than 30 days after the end of the previous flare-up, versus NHS. (Subjects without 2 WBCTs post-restart in Study 202 Part C where the first is at least 30 days after the end of the previous flare-up are not included.)

These models are run with 3 covariates in addition to treatment – baseline age, sex, total HO – and with 5 covariates in addition to treatment – baseline age, sex, total HO, CAJIS, time since last flare up.

In addition to these regression-based techniques, FDA has requested that propensity-score-based methods, including matched pairs analyses and weighted analyses also be performed to compare annualized new HO in Study 202 versus NHS. Propensity scores are being generated using the set of 5 covariates listed above.

Additional analyses are also being performed, including those that pool Study 202 Part B and Part C as well as several in which Study 202 and Study 301 data are pooled.

3.5 Handling of Dropouts or Missing Data

As there is no effective treatment for subjects with FOP, it is assumed they will be highly motivated to adhere to the protocol and treatment visits. Thus, it is expected that there will be minimal missing data, and most subjects will complete the study. The efficacy analysis will be performed using observed data only. Missing efficacy data will not be imputed.

3.7 Handling of Partial Dates for Medications

When determining prior or concomitant medications, partial start dates of prior and concomitant medications will be assumed to be the earliest possible date consistent with the partial date.

For the purposes of analysis, incomplete medication start and stop dates will be imputed.

- If the start date and end date are completely missing, then the start date is imputed as the date of informed consent, the end date is the date of last assessment for the subject, and the medication would be considered as both prior and concomitant.
- If a medication start date is incomplete, January will be imputed for missing month and/or the first day of the month will be imputed for missing day.
- If a medication stop date is incomplete, December will be imputed for missing month and the last day of the month will be imputed for missing day.
- If the imputed medication stop date is after the date of study completion, the date of study completion will be used instead.

3.8 Handling of Partial Dates for Adverse Events

- If the start date is completely missing, the start date is imputed as the date of first dose and the AE is considered treatment emergent and assigned to the non-flare-up dosing period.
- If the day and month of the start date are missing and the start year is the same as the year of first dose, the start date is imputed as the date of first dose and the AE is considered treatment emergent and assigned to the non-flare-up dosing period.
- If the start year is prior to the year of first dose, the start date is imputed as January 1 of the year and the AE is not considered treatment emergent.
- If the day of the start date is missing and the start month and year is within a period of time within a flare-up cycle, the start date is imputed as the start date of the flare-up cycle in the same month as the AE, and the AE is considered treatment emergent and assigned to the flare-up dosing period.
- Otherwise, if the day of the start date is missing and the start month and year is on or after the date of first dose, the start date is imputed as the date of first dose or the first day of the month of the AE, whichever is later, and the AE is considered treatment emergent and assigned to the non-flare-up dosing period. Otherwise, if the start month and year is before the month and year of first dose, then the start date is imputed as the first day of the month of the AE, and the AE is not treatment emergent.
- Partial AE end dates will be imputed as the last day of the month or year for missing end dates. Completely missing end dates will be imputed as the date of last known treatment exposure for the subject.

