4.1 Enrolled Population

The Enrolled Population will include all subjects enrolled in Part C.

Unless stated, analysis for Enrolled Population will be presented by groups: PVO 20/10 mg Only, nonflare-up PVO 5 mg, PVO total, and Never Received PVO Treatment. The PVO 20/10 mg Only group only includes subjects who didn't take PVO 5 mg.

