7.1 Adverse Events

Adverse events will be recorded from the time informed consent (Part C Study Day 1) is signed through study completion. All AEs will be coded to system organ class and preferred term using will be coded using a current version of MedDRA **Study Drug Related Adverse Events:**

At least possibly related AEs are defined as AEs assessed by the Investigator as possibly, probably, or definitely related to study drug.

Adverse events that require Common Terminology Criteria for Adverse Events (CTCAE) grading (Version 4.03, 14 June 2010) as indicated on the eCRF are considered to be retinoid-associated AEs.

Adverse Events Analysis Periods:

All AEs collected during Part C from the time informed consent is signed are considered as treatment emergent adverse events (TEAEs).

TEAEs will be summarized by period (Non-Treatment Period, Non-Flare-up Treatment Period, and Flare-up Treatment Period, Total Treatment Period) and in total.

a) Flare-up treatment period

Adverse events with start date on or after Flare-up Cycle Day 1 and on or before the date of completion for the Flare-up treatment will be attributed to the Flare-up treatment period.

b) Non-Flare-up Treatment Period

Adverse events with start date on or after first Non-Flare-up dose date in Part C for which the subjects are not undergoing flare-up treatment will be attributed to the Non-Flare-up Treatment Period.

Non-Flare-up Treatment Period is period that subjects taking non-flare-up dose including non-flare-up dose interruption periods. All flare-up cycles are excluded.

c) Non-Treatment Period

Adverse events with start date on or after Study Day 1 that are not attributed to the flare-up or non-flare-up treatments will be attributed to the Non-Treatment Period.

Non-Treatment Period are period that subjects are receiving neither non-flare-up and nor flare-up treatment. In Part C, it is the period starting from Part C Study 1 to the day before first study drug dosing date (regardless of whether non-flare-up or flare-up based treatment), and the period from date of study drug discontinuation to end of study or study discontinuation date.

Adverse Events Summary:

The incidence of the following TEAEs will be summarized with counts and percentages of subjects (overall and by MedDRA system organ class and preferred term):

Adverse Event Variables

Adverse Event Observation Periods

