- TEAEs are AEs with (first dose date of study drug during 202 C) \leq (AE start date) \leq (last dose date of study drug +7 days for all AEs, i.e., non-serious and serious AEs).
 - A chronic TEAE is a TEAE with an onset date during chronic treatment
 - A flare-up TEAE is a TEAE with an onset date during flare-up treatment
- Post-treatment AEs are AEs with a start date $>$ last dose date in Part C + 7 days for All AEs (non-serious and serious AEs).
 - Any AEs
 - Any post treatment AEs
 - Any TEAEs
 - Any TEAEs by maximum severity
 - Any TEAEs at least possibly related to study drug
 - Any TEAEs at least possibly related to study drug by maximum severity
 - Any serious adverse events (SAEs)
 - Any TEAEs leading to dose modification
 - Any TEAEs leading to interruption of study drug
 - Any TEAEs leading to discontinuation of study drug
 - Any TEAEs leading to discontinuation from study

Data listings will be provided for

- All TEAEs
- All post treatment AEs

- SAEs
- SAEs for premature physcal closure and bone safety
- Deaths
- TEAEs leading to dose modification of study drug
- TEAEs leading to interruption of study drug
- TEAEs leading to discontinuation of study drug
- TEAEs leading to discontinuation of study
- AEs ongoing at date of informed consent signed in Part C

Part C Study Day and/or Flare-up Day for AE start and stop dates will be included on AE listings as appropriate.

Adverse event severity will be assessed and reported according to criteria defined in the protocol (mild, moderate, severe). Adverse event causality will also be assessed in terms of relationship to study drug and reported according to criteria described in the protocol (not related, possibly related, probably related, definitely related).

Deaths

Deaths after the first dose of study drug are either on-treatment or post-treatment:

- Deaths on-treatment: deaths occurring after the first dose of study drug and up to 7 days after the last dose of study drug
- Death post-treatment: deaths occurring more than 7 days after the last dose of study drug until 30 days after last dose of study drug

The SAE, including death, reporting period for the non-flare-up-based treatment and the flare-up-based treatment begins at the time of informed consent and continues through study completion (including Part D) + 30 days.

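### Part C SAP 3.8 assigns every missing-day AE outside a flare-up-cycle month to the 5 mg period once dosing has begun, even after permanent discontinuation or in subjects who never took 5 mg

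*SAP*

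**What the plan says.** Part C SAP section 3.8 treats a missing start day in two steps. The first applies "If the day of the start date is missing and the start month and year is within a period of time within a flare-up cycle". For these events the start becomes the start date of the cycle in the AE's month, "and the AE is considered treatment emergent and assigned to the flare-up dosing period". The second is the residual rule and applies "if the day of the start date is missing and the start month and year is on or after the date of first dose". Here the start becomes the first-dose date or the first of the AE month, "whichever is later, and the AE is considered treatment emergent and assigned to the non-flare-up dosing period".

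A fully missing start date, and a year-only date in the year of first dose, are set to the first-dose date and also go to the non-flare-up period. For end dates the rule is: "Completely missing end dates will be imputed as the date of last known treatment exposure for the" subject.

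For complete dates, section 7.1 works differently. An event attributed to neither regimen belongs to the Non-Treatment Period, which includes "the period from date of study drug discontinuation to end of study or study discontinuation date". Post-treatment events are those that start later than "last dose date in Part C + 7 days for All AEs (non-serious and serious AEs". Interruptions of 5 mg dosing count as non-flare-up time. Section 4.1 sets up a treated group without 5 mg exposure: "The PVO 20/10 mg Only group only includes subjects who didn't take PVO 5 mg".

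**The concern.** The residual rule tests only a lower bound, the first dose. It can never return the Non-Treatment Period or post-treatment, and it does not ask whether the subject ever took 5 mg. An event can therefore change column only because its day is missing, even when the reported month alone shows that it happened off drug.

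Sections 7 and 7.1 present AEs by treatment period, so the column is the result. Off-drug time is also a substantial part of this report:

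- Section 10 puts the focus of the final study report on data after 28 February 2020.
- Section 1.1 includes subjects who did not restart.
- Section 2.3 says children under 14 stopped on 4 December 2019 and were not restarted.
- Section 2.2 has Part D follow skeletally immature subjects for up to 2 years without drug, with AEs among its assessments.

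**Working it through.** The plan states no figure to reproduce, so the check is one of logic. I applied the missing-day rules of section 3.8, in their stated order, to five hypothetical subjects and classified the same dates by section 7.1. All dates are assumptions. First dose is read as first dose in Part C.

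| Case | Section 3.8 | Section 7.1 |
|---|---|---|
| A. 5 mg subject, cycle 1 Mar to 23 May 2019, AE in Mar 2019 | 1 Mar 2019, flare-up, treatment emergent | Flare-up, treatment emergent |
| B. 5 mg subject, permanent stop 24 Jan 2020, AE in Mar 2020 | 1 Mar 2020, non-flare-up, treatment emergent | Non-Treatment Period, post-treatment |
| C. 20/10-only subject, cycles 1 Jun to 23 Aug 2018 and 1 May to 23 Jul 2019, AE in Jan 2019 | 1 Jan 2019, non-flare-up, treatment emergent | Non-Treatment Period, treatment emergent |
| D. Same subject as C, AE in Dec 2019 | 1 Dec 2019, non-flare-up, treatment emergent | Non-Treatment Period, post-treatment |
| E. As A, AE in Apr 2019 | Flare-up, treatment emergent, no start date defined | Flare-up, treatment emergent |

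- **B:** 24 Jan 2020 + 7 days = 31 Jan 2020. The imputed 1 Mar 2020 is 7 + 29 + 1 = 37 days after last dose, and 37 − 7 = 30 days past the limit.
- **C:** section 7.1's closing description of the Non-Treatment Period does not list gaps between cycles. Its general rule covers them, since it takes any event attributed to neither regimen. The event lies between first dose and last dose + 7 days, so only the period is wrong.
- **D:** 23 Jul 2019 + 7 days = 30 Jul 2019. The imputed 1 Dec 2019 is 8 + 31 + 30 + 31 + 30 + 1 = 131 days after last dose, and 131 − 7 = 124 days past the limit.
- **E:** the rule asks for a cycle start in the AE's month. The cycle began in March, so no such date exists for an April event. The period is still correct.

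B, C and D are placed on 5 mg against the plan's own period definitions. A and E go to the correct period.

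**Fully missing date, 20/10-only subject.** With first dose on 1 Jun 2018, section 3.8 imputes that day, which is the first day of a flare-up cycle, and then assigns the event to the non-flare-up period. Section 7.1 attributes an event starting on that day to flare-up treatment. A year-only date in 2018 gives the same conflict.

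**Missing end date.** In case B a completely missing end date becomes 24 Jan 2020, 37 days before the imputed start.

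**The case against.** The strongest defence is that partial-date rules are meant to be conservative and that calling doubtful events treatment emergent is the cautious choice. That suits an event whose timing relative to dosing is unknown. It does not suit one whose reported month excludes dosing, or a subject who never took the regimen, and it lowers the post-treatment count.

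Several limits on the point do stand:

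- A reader might infer that every missing-day event after first dose becomes a 5 mg event. It does not: months within a flare-up cycle are sent to the flare-up period first (cases A and E).
- A reader might infer that all off-drug events are misplaced. Section 7.1 counts 5 mg interruptions as non-flare-up time even for complete dates, so for subjects who paused and restarted the two sections agree.
- A reader might infer a one-way shift into the 5 mg column. This is not shown: a month that overlaps a cycle goes wholly to flare-up, even if most of it was spent on 5 mg.
- A reader might take the cycle rule to back-date an event to a cycle start in an earlier month. Read literally, it yields no date.
- Section 7.1 is not consistent itself. It first calls every Part C event from consent treatment emergent, then limits the term to first dose through last dose + 7 days. Under the first definition the treatment-emergent label is no conflict, but the period assignment is still wrong.
- The end-date defect reaches only listings. The planned AE summaries are incidences, and no analysis of AE duration is planned.

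**Conclusion.** The point holds in limited form. For a missing-day event on or after first dose and outside any cycle month, section 3.8 always returns the 5 mg period. That is wrong when the month lies wholly after permanent discontinuation, and when the subject took only 20/10 mg. The fully missing and first-year year-only defaults share the second fault. The undefined start date in case E and an end date before the start are secondary defects.

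The size cannot be computed, because the document gives no frequency of partial AE dates; the affected events may be few. The longest exposed stretch, up to 2 years in Part D against a 7-day limit, concerns only skeletally immature subjects.

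The Non-Treatment result for case B assumes that a stop never followed by a restart is a discontinuation, not an open-ended interruption; the SAP does not say when one becomes the other. The post-treatment result does not need that assumption, since it depends only on the last dose date.

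**What to change.** Amend section 3.8 as follows:

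1. Keep the flare-up preference when the AE month and a cycle overlap, and impute the later of the cycle start and the first of the AE month.
2. Limit the residual rule to subjects who took 5 mg and to months that overlap that subject's own non-flare-up treatment period, interruptions included as in section 7.1.
3. Send all other months after first dose to the Non-Treatment Period, and label the event post-treatment when its earliest possible date is after last dose + 7 days.
4. Keep the non-flare-up default for fully missing and first-year year-only dates only in subjects who took 5 mg. In 20/10-only subjects assign these events to the flare-up period, which matches the imputed first-dose date.
5. Never impute an end date before the start date.
6. Reconcile the two definitions of treatment emergent in section 7.1, since step 3 depends on which one governs.

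The cost is SAP wording and a small change to the AE derivation program. No new data are needed.
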